7. STUDY ASSESSMENTS AND PROCEDURES

7.1. Pharmacokinetic Assessments

7.1.1. Pharmacokinetic Blood Sample Collection and Processing

Blood samples for PK analysis of each substrate (caffeine/paraxanthine, omeprazole, and S-warfarin) and LOXO-305 plasma levels will be collected at the timepoints specified in [Appendix 4](#). The exact time of the study drug administration and the actual time of blood sampling for PK analysis will be recorded on the eCRF.

Processing, storage, and shipping instructions for these PK blood samples will be provided in a separate Laboratory Manual. The number of blood samples and total blood volume required for PK testing is presented in [Appendix 3](#).

7.1.2. Analytical Methodology

Plasma concentrations of each substrate (caffeine/paraxanthine, omeprazole, and S-warfarin) and LOXO-305 will be determined using validated bioanalytical methods. Specifics of the bioanalytical methods will be provided in a separate document.

7.2. Genotyping

A blood sample for genotyping to exclude subjects who are non- and slow CYP2C9 (CYP2C9 *2/*3 or CYP2C9 *3/*3 genotypes) and CYP2C19 (CYP2C19 *2/*2, CYP2C19 *2/*3, or CYP2C19 *3/*3 genotypes) metabolizers will be collected at the Screening.

Blood volume required for genotyping is presented in [Appendix 3](#).

7.3. Safety and Tolerability Assessments

Safety evaluations may be repeated at the discretion of the Investigator (or designee) or Sponsor.

Every effort will be made to schedule and perform the procedures in accordance with the nominal time, giving considerations to appropriate posture conditions, practical restrictions, and any other procedures to be performed at the same timepoint. The order of priority for scheduling procedures around a timepoint is (in order of priority):

- dosing
- PK blood sampling
- vital sign measurements *
- 12-lead ECGs *
- blood and urine samples for clinical laboratory evaluations
- physical examination.

* When vital sign measurements and 12-lead ECGs are scheduled at the same time as PK blood sampling, the PK blood sampling will be obtained at the scheduled timepoint, and the

vital sign measurements followed by 12-lead ECGs will be obtained prior to and as close as possible to the scheduled PK blood sampling.

7.3.1. Adverse Events

Adverse event definitions; assignment of severity, causality, action taken, and outcome; and procedures for reporting SAEs are detailed in [Appendix 1](#).

Subjects will be asked a non-leading HDYF? question such as “Have there been any changes in your health status since Screening/since you were last asked?” at the timepoints specified in [Appendix 4](#) (ie, at Screening [after the ICF is signed], at Check-in [Day -1], at each postdose vital sign measurement, and at an appropriate time for all other days). Subjects will also be encouraged to voluntarily report AEs occurring at any other time through the EOS.

Adverse events, whether volunteered, identified by the subject’s responses to HDYF? inquiries, or noted on physical examination, ECG, vital sign measurements, or clinical laboratory evaluations, will be recorded throughout the study (ie, from signing of the ICF until EOS [or ET if the subject discontinues from the study and does not complete a follow-up phone call]), either as subject medical history (if the event is reported as beginning prior to signing of the ICF or if the event occurs prior to study drug administration on Day 1 and is assessed as not related to study procedures by the Investigator [or designee]) or as AEs (if the event occurs after signing of the ICF but prior to study drug administration on Day 1 and is assessed as related to study procedures by the Investigator [or designee], or if the event occurs after study drug administration on Day 1 through EOT or ET regardless of relationship to study drug). From EOT or ET through EOS, only AEs assessed as related to study drug by the Investigator (or designee) are to be reported. All SAEs that develop from the time of ICF signing until EOS (or ET, if the subject discontinues from the study and does not complete a follow-up phone call) are to be reported.

Unless a subject withdraws consent or is withdrawn from the study and does not complete the follow-up phone call, all subjects must be followed until EOS. Subjects with AEs that are assessed as related to study drug by the Investigator (or designee) which are ongoing at EOS may continue to be followed until the symptoms or value(s) return to normal, or acceptable levels, as judged by the Investigator (or designee) and confirmed by the Sponsor. The Investigator (or designee) should use appropriate judgment in ordering additional tests as necessary to monitor the resolution of events. The Sponsor may request that additional safety tests be performed.

Subjects will receive a follow-up phone call 7 days (\pm 2 days) after EOT or ET to determine if any SAE or drug-related AE has occurred since the EOT or ET visit.

At all times, a subject may be required to remain at the CRU for longer at the discretion of the Investigator (or designee).

Any event that meets the criteria of a suspected unexpected serious adverse reaction (SUSAR) will be reported to the Institutional Review Board (IRB) according to CRU policy by the Investigator (or designee) and to regulatory authorities by the Sponsor (or Sponsor designee) according to regulatory authority requirements. Refer to Reference Safety Information in the current [IB¹](#) for LOXO-305 for additional safety information.

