1.4.2. Pharmacokinetics

As of September 30, 2020, PK data were available from 181 patients enrolled in the LOXO-BTK-18001 study. Steady-state PK parameters of LOXO-305 in these cancer patients could be derived from data collected on Cycle 1 Day 8 (Figure 1), and are shown in Table 1. These data show that LOXO-305 is absorbed after oral administration with a median time to maximum observed plasma concentration (t_{max}) of approximately 2 hours and low clearance (Table 1). Due to the limited sampling interval (0-8 hours), imputation for the 24-hour sample was made from Cycle 1 Day 8 predose sample, leading to an estimated plasma half-life of

approximately 20 hours. Maximum observed plasma concentration and area under the plasma concentration-time curve (AUC) of LOXO-305 showed increase proportional to dose (Figure 2). Following administration of the recommended Phase 2 dose (RP2D) 200 mg QD, mean trough plasma levels of LOXO-305 exceeded the concentration required for 96% inhibition of BTK in vitro ($IC_{50} = \text{[CC]} \text{ ng/mL}$, $IC_{96} = \text{[CC]} \text{ ng/mL}$). Further details may be found in the IB.¹

Pharmacokinetic data following oral administration of a 200-mg dose of LOXO-305 in tablet form in healthy volunteers in the LOXO-BTK-20014 study indicate that there was little effect of either a standard meal or the proton pump inhibitor omeprazole on the PK of LOXO-305.

**Table 1: Pharmacokinetic Parameters of LOXO-305 in Cancer Patients
(Study LOXO-BTK-18001) at Steady State (Cycle 1 Day 8)**

[figure not shown]
Dose Level	N	C_{\max} (ng/mL) Geo mean (%CV)	t_{\max} (h) Median (min, max)	AUC_{0-8} (ng*h/mL) Geo mean (%CV)	AUC_{0-24} (ng*h/mL) Geo mean (%CV)	CL/F (L/h) Geo mean (%CV)	$t_{1/2}$ (h) Geo mean (%CV)	Ratio AUC_{0-8} Day 8/Day 1 Geo mean (%CV)
25 mg QD	5	734 (11.0%)	2 (1, 8)	4240 (12.4%)	9800 (25.8%)	1.55 ^a (69.6%)	18.2 ^a (60.1%)	1.44 (23.0%)
50 mg QD	6	1420 (19.2%)	1.5 (1, 4)	8660 (24.7%)	20100 (34.9%)	2.62 ^b (36.7%)	17.6 ^b (39.6%)	1.51 (25.9%)
100 mg QD	9	3910 (35.6%)	2 (1, 4)	22000 (37.2%)	52400 (39.7%)	0.968 ^c (63.0%)	22.2 ^c (33.9%)	1.88 (42.8%)
150 mg QD	20	4680 (29.1%)	2 (1, 8)	28000 (29.6%)	64400 (39.6%)	1.36 ^d (66.7%)	18.1 ^d (51.8%)	1.74 (24.9%)
200 mg QD	99	5770 (47.7%)	2 (1, 8)	36900 (40.8%)	91000 (42.0%)	1.14 ^e (61.8%)	19.9 ^e (56.2%)	1.69 ^h (29.6%)
250 mg QD	25	8100 (28.1%)	2 (1, 4)	49700 (31.3%)	111000 (38.7%)	1.26 ^f (1.08%)	17.4 ^f (50.6%)	1.68 (24.5%)

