1.6. Risk Assessment

Subjects in the current study will not receive any health benefit (beyond that of an assessment of their medical status) from participating in the study. The risks of participation are primarily those associated with adverse reactions to the study treatments, although there may also be some discomfort from collection of blood samples and other study procedures. The dose of LOXO-305 administered in this study is not anticipated to induce any potential risk to subjects participating in this study as the dose does not exceed the highest dose safely administered in first-in-human study or healthy volunteer studies.¹ More information about the known and expected benefits, risks, and reasonably anticipated AEs associated with LOXO-305 may be found in the IB.¹

There is a potential risk that multiple doses of LOXO-305 may lead to decreases in white blood cells including neutrophils, lymphocytes, monocytes, and eosinophils. Therefore, to mitigate any potential immunosuppressive risks during the ongoing SARS-CoV-2 (COVID-19) pandemic, subjects will remain in the Clinical Research Unit (CRU) for 96 hours postdose (Day 23) to allow for LOXO-305 elimination. In addition, subject's hematology laboratory results will be reviewed prior to discharge from the CRU. More information about the known and expected benefits, risks, and reasonably anticipated AEs associated with LOXO-305 may be found in the IB.¹

The dose of caffeine, omeprazole, vitamin K, and warfarin administered in this study are not anticipated to induce any potential risk or benefit to subjects participating in this study, as they are single doses administered according to the dosing recommendations in the full prescribing information.

The safety monitoring practices employed will include AE reporting, vital sign measurements, 12-lead ECGs, clinical laboratory evaluations, and physical examinations, and are considered adequate to protect the subjects' safety.

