- o. Clinical chemistry panel (fasted for at least 8 hours), coagulation parameters, hematology panel, and UA will be performed at Screening, Check-in (Day -1), Day 2 (24 hours postdose on Day 1), Day 6 (predose), Day 12 (predose), Day 15 (predose), Day 17 (predose), Day 20 (24 hours postdose on Day 19), and Day 22 (72 hours postdose on Day 19, if the subject completes the study [EOT]), or on the day of ET. At ET or the day before EOT (Day 22), subjects are not required to be fasted prior to clinical laboratory evaluations.
- p. Testing for COVID-19 will be conducted at a minimum at Screening and Check-in (Day -1). Testing for COVID-19 may also be conducted periodically during the subject's CRU confinement, at the discretion of the Investigator (or designee). Tests will be performed by rapid polymerase chain reaction or equivalent.
- q. Urine drug screen for drugs of abuse (including cotinine) and alcohol screen (urine or breath).
- r. Prior and concomitant medication administration will be recorded beginning at informed consent. In addition, all Investigator-approved prescription and over-the-counter medications taken by a subject within 14 days or 5 half-lives (if known), whichever is longer, prior to Day 1 will be recorded on the subject's electronic CRF.
- s. Female subjects only. Performed at Screening, Check-in (Day -1), and Day 22 (72 hours postdose on Day 19), if the subject completes the study (EOT) or on the day of ET.
- t. Post-menopausal female subjects only.
- u. End of Treatment is defined as when the subject is released from the CRU following completion of all assessments through Day 23. Early Termination is defined as when the subject is released from the CRU if the subject terminates the study early. Vital sign measurements, ECG, and abbreviated physical examination results are to be available for review by the Investigator (or designee) prior to subject release from the CRU on Day 23 (EOT) or ET. Clinical laboratory results (for clinical chemistry, hematology, coagulation, and UA) and serum pregnancy test results (female subjects only) are to be available for review by the Investigator (or designee) prior to subject release from the CRU at the EOT visit and prior to subject release from the CRU at the ET visit if available.

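### For early terminators, all-cause collection of non-serious AEs ends at release with no minimum time since the last dose (completers have 96 h), and Section 1.6 and footnote u disagree on hematology review before release

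*Protocol*

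**What the plan says.** **AE window.** Protocol Section 7.3.1 counts an event as an AE "if the event occurs after study drug administration on Day 1 through EOT or ET regardless of relationship to study drug". After that point, "From EOT or ET through EOS, only AEs assessed as related to study drug by the Investigator (or designee) are to be reported". Serious events run further: "All SAEs that develop from the time of ICF signing until EOS (or ET, if the subject discontinues from the study" without completing the follow-up call). The synopsis, Section 3.1, Appendix 4 footnote j and SAP Section 4 carry the same rule. The call is made 7 ± 2 days after EOT or ET and asks about SAEs and drug-related AEs only.

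**When the window closes.** For a completer, EOT is Day 23. For anyone else, Appendix 4 footnote u applies: "Early Termination is defined as when the subject is released from the CRU if the subject terminates the study early". No minimum time since the last dose is attached.

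**Hematology.** Section 1.6 names a possible fall in white cells as a risk and gives two mitigations. One is that "subjects will remain in the Clinical Research Unit (CRU) for 96 hours postdose (Day 23) to allow for LOXO-305 elimination". The other is that the subject's "hematology laboratory results will be reviewed prior to discharge from the CRU". Footnote u requires laboratory results for review before release at EOT, but for early terminators only "prior to subject release from the CRU at the ET visit if available".

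**The concern.** One rule is written for both groups, but it closes at an event (release) and not at a time since dosing. For completers the two coincide at 96 h. An early terminator may be released on a dosing day or the day after, and all-cause reporting of non-serious events stops there. AE ascertainment after the last dose then depends on whether the subject completed. Safety and tolerability is the study's only secondary objective. The SAP (Section 8.6.1) tabulates treatment-emergent AEs by treatment with no allowance for unequal follow-up.

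The hematology point is separate. Section 1.6 presents the review before discharge as a safeguard for everyone, while the schedule makes it conditional for one group. A reader cannot tell which statement governs an early terminator, or what happens to a result that arrives after that person has left.

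**Working it through.** **1. Reproduce the plan's figure.** Last LOXO-305 dose Day 19, EOT Day 23: (23 − 19) × 24 h = 96 h. This matches Section 1.6.

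**2. All-cause window for non-serious AEs after the last dose.**

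- Completer: 96 h.
- Early terminator released on a dosing day: about 0 h.
- Early terminator released the next day: about 24 h.
- Guaranteed minimum for early terminators: none stated.

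**3. Drug still present.** The inputs are in Protocol Section 1.4.2. The text describes limited 0–8 h sampling with an imputed 24 h value, "leading to an estimated plasma half-life of" approximately 20 h. Table 1 gives 19.9 h at 200 mg QD (geometric mean, CV 56.2%). Fraction remaining = 0.5^(t / half-life), assuming mono-exponential decline. For a range I take ±1 geometric SD, assuming log-normal half-lives: s = √ln(1 + 0.562²) = 0.524, so 19.9 × e^(±0.524) gives 11.8 h to 33.6 h.

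| Time since last dose | 11.8 h | 19.9 h | 33.6 h |
|---|---|---|---|
| 24 h | 24.4% | 43.3% | 61.0% |
| 48 h | 5.9% | 18.8% | 37.2% |
| 96 h | 0.4% | 3.5% | 13.8% |

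96 h is 96 / 19.9 = 4.8 half-lives. The gap between 24 h and 96 h holds across the range.

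**4. What is still collected after ET.**

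| Event after release | Call completed | No call |
|---|---|---|
| SAE, any cause | reported to End of Study | collection ends at ET |
| Non-serious, related | reported to End of Study | collection ends at ET |
| Non-serious, not judged related | not reported | collection ends at ET |

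With a completed call, the loss is the third row only.

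**5. Can the existing call cover the gap?** The call falls 5 to 9 days after release. The earliest is 5 × 24 = 120 h after release, which is always beyond 96 h from the last dose. Time from last dose to call is 5 to 9 days for same-day release, 6 to 10 days for next-day release, and 4 + 5 = 9 to 4 + 9 = 13 days for completers. One question at the call can therefore cover the whole 96 h.

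**6. Hematology passages side by side.** Section 1.6 attaches no condition and no day to the hematology sentence. Footnote o schedules hematology on the day of ET. Section 4.6 makes ET assessments a best effort. Footnote u then requires results before release at ET only when they are to hand. The first statement has no exception and the last contains one.

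**The case against.** **The AE rule is consistent and contradicts nothing.** This stands. Section 1.6 is silent on AE collection, and every statement of the AE rule agrees. A reader might infer that the AE sentence conflicts with the 96 h stay, but the documents do not support that. The AE point is an avoidable difference in ascertainment, not an inconsistency. The 96 h sentence, tagged Day 23, can also fairly be read as describing completers only.

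**Early terminators need not be intolerant.** This stands. Section 4.6 lists AEs as one withdrawal reason among several, and anyone leaving before Day 6 has had no LOXO-305. A reader might infer that tolerability will look too favourable. No dropout rate is given, so neither the direction nor the size of a bias is shown.

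**An early event would still be caught as related.** This stands in part. Under Appendix 1, an AE is not related only if the time course rules out causality and another cause is suspected, which is hard to meet while drug is present. But related requires that no other cause can be identified. A bruise or mild infection with a plausible alternative cause fits neither definition cleanly, so its capture is uncertain. It would be too strong to say that it would never be recorded.

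**A reviewer is named.** This stands. Footnote u assigns the review to the Investigator or designee, Section 7.3.1 allows further tests, and a subject may be kept longer at the Investigator's discretion. Only the handling of a result received after release is unstated.

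**The half-lives come from patients.** This stands. Sampling was limited and the CV is 56.2%. Residual drug also does not measure missed events.

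**Conclusion.** The point holds as a modest gap in data capture plus a wording conflict. All-cause collection of non-serious AEs after the last dose is 96 h for completers and has no floor for early terminators. If the call is completed, only non-serious events not judged related can be lost. If it is missed, all collection ends at ET for everyone in that position.

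The effect on the safety summary cannot be sized from the documents. For scale only, with the planned maximum of 16 subjects, one subject with an unrecorded event is 1/16 = 6.25 percentage points. The residual-drug figures rest on patient half-lives, mono-exponential decline and log-normal variation. They show why release at 24 h differs from release at 96 h and nothing more.

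On hematology, the conflict is between Section 1.6 and footnote u alone. The documents do not settle which statement governs early terminators, and this review takes no position on that.

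**What to change.** **AE capture.** In Protocol Section 7.3.1, the synopsis, Section 3.1, Appendix 4 footnote j and SAP Section 4, report AEs of any cause through the later of EOT/ET and 96 h after the last dose. For early terminators, collect them with one added question at the follow-up call they already receive. Completers are unaffected, because their window already ends at 96 h. The cost is wording in five places and one question. The drawbacks are that these events rest on recall 5 to 9 days after release, so ascertainment will still not equal that of confined subjects, and that nothing is gained for subjects who miss the call.

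**Hematology.** Reconcile Section 1.6 with footnote u for early terminators, and state how a result that arrives after release is handled. Which rule applies is for the sponsor and investigator to decide. The cost is wording only.

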7.3.2. Clinical Laboratory Evaluations

Clinical laboratory evaluations (clinical chemistry panel [fasted at least 8 hours; at ET or the day before EOT, subjects are not required to be fasted prior to clinical laboratory evaluations], coagulation parameters, hematology panel, TSH [Screening only], HbA1c [Screening only], eGFR [Screening and Check-in (Day -1)], and UA) will be collected at the timepoints specified in [Appendix 4](#).

Screens for HCV antibody, HBsAg, HBV IgM core antibody, and HIV antibody will be performed at Screening.

Testing for COVID-19 via PCR (or equivalent) will be performed at the timepoints specified in [Appendix 4](#). Testing for COVID-19 may also be conducted periodically during the subject's CRU confinement, at the discretion of the Investigator (or designee). Further details regarding COVID-19 testing (including procedures for subjects who test positive at any time throughout CRU confinement) are specified in a separate document.

A urine drug screen for selected drugs of abuse (including cotinine) and an alcohol screen (urine or breath) will be performed at Screening and repeated at Check-in (Day -1) for all subjects. A serum qualitative pregnancy test (female subjects only [serum quantitative may be used for confirmation, if needed]) and an FSH test (post-menopausal female subjects only) will be performed at the timepoints specified in [Appendix 4](#).

The number of blood samples and total blood volume required for clinical laboratory evaluations are presented in [Appendix 3](#). A list of the specific evaluations is in [Appendix 2](#).

7.3.3. Vital Signs

Vital sign measurements (including body temperature, respiratory rate, oxygen saturation, and supine BP and pulse rate) will be obtained at the timepoints specified in [Appendix 4](#).

Blood pressure and pulse rate measurements should be performed using the same arm for each reading and measurements should be taken after the subject has been resting in the supine position for at least 5 minutes.

When vital sign measurements are scheduled at the same time as PK blood draws, the PK blood draws will be obtained at the scheduled timepoint, and the vital sign measurements will be obtained prior to and as close as possible to the scheduled PK blood draw.

7.3.4. 12-lead Electrocardiogram

A 12-lead ECG (including HR, PR, RR, QRS, and QT interval parameters) will be obtained after the subject has been resting for at least 10 minutes in the supine position at the timepoints specified in [Appendix 4](#). The QT interval will be corrected for HR by Fridericia's ($QTcF = QT/[RR]^{1/3}$) formula.

When 12-lead ECGs are scheduled at the same time as PK blood draws, the PK blood draws will be obtained at the scheduled timepoint, and the 12-lead ECGs will be obtained prior to and as close as possible to the scheduled PK blood draw.

7.3.5. Physical Examination

A complete or abbreviated physical examination will be performed at the timepoints specified in [Appendix 4](#). Complete physical examinations will evaluate general appearance and the following body systems/organs: dermatological; head and eyes; ears, nose, mouth, and throat; pulmonary; cardiovascular; abdominal; lymphatic; musculoskeletal/extremities; and neurological. Weight and height will be reported (height only reported during Screening). Abbreviated physical examinations will evaluate general appearance and the following body systems/organs: dermatological; pulmonary; cardiovascular; abdominal; and neurological.

